4.0 INTRODUCTION

4.1 Background

Critically ill patients who require enteral feeding frequently have reduced gastrointestinal (GI) motility, develop enteral feeding intolerance, which can lead to several complications including not meeting daily calorie and protein requirements [1]. The addition of malnutrition in these patients is associated with impairment of immunological function, increased risk of infection, prolongation of mechanical ventilation, increased length of intensive care unit and hospital stay, and ultimately higher mortality [2,3].

TAK-954 is being developed for short-term use with enteral feeding to treat critically ill patients with enteral feeding intolerance. TAK-954 is a highly selective and potent serotonin type 4 (5-HT4) receptor agonist that exhibits prokinetic activity throughout the GI tract [4].

TAK-954 has been investigated in healthy subjects at single oral doses from 0.1 to 20 mg, multiple oral doses from 0.2 to 10 mg daily for 10 days, and multiple intravenous (IV) doses from 0.1 to 0.5 mg daily for 5 days. TAK-954 has been shown to undergo oxidative metabolism in vitro in human liver microsomes, although it was relatively stable when incubated with cryopreserved human hepatocytes (half-life [$t_{1/2}$])>17 hours).

The purpose of this trial is to investigate the effect of a potent CYP3A4 inhibitor on the PK of IV TAK-954 in healthy males and females. Itraconazole has been chosen as it is recommended by the Food and Drug Administration (FDA) and European Medicines Agency (EMA) as a suitable potent cytochrome P-450 (CYP) 3A4 inhibitor for use in drug-drug interaction (DDI) studies. An IV dose of 0.2 mg TAK-954 daily has been selected as a dose that is predicted to be within the clinically relevant range, but is lower than the maximum multiple IV dose (0.5 mg) that has been investigated so far, to allow for any increases in exposure that may be observed with metabolic inhibition.

Please refer to the TAK-954 Investigator's Brochure for complete information on the investigational product and the most recent itraconazole product insert for the appropriate region.

This trial will be conducted in compliance with the protocol, Good Clinical Practice (GCP), and the applicable regulatory requirement(s).

4.2 Rationale for the Proposed Trial

This is a phase 1, single-sequence, open-label, 2-period crossover trial in 10 healthy male and female (non-childbearing potential) subjects. The trial is designed to investigate the effect of a potent CYP3A4 inhibitor (itraconazole) on the PK of TAK-954. TAK-954 will be administered as a single 60-minute IV infusion.

4.3 Benefit/Risk Profile

As this is a trial in healthy subjects, there is no expected clinical benefit to the trial participants. Potential risks are based on clinical findings, the mechanism of action, and nonclinical findings.

There is minimal risk associated with trial procedures including phlebotomy (limited to <500 mL) and noninvasive procedures including vital sign assessments and ECGs. The principal mitigation for these risks includes appropriate selection of the trial populations, the CRU setting, which permits close monitoring and rapid institution of appropriate care as needed, and the specified monitoring procedures. Overall, the risk:benefit is considered appropriate for this trial.

5.0 TRIAL OBJECTIVES AND ENDPOINTS

5.1 Objectives

5.1.1 Primary Objective

The primary objective of the trial is to evaluate the effect of the potent CYP3A4 inhibitor itraconazole on the single-dose PK of TAK-954.

[figure not shown]
5.1.2 Secondary Objective

The secondary objectives of the trial are to evaluate the safety of single-dose IV doses of TAK-954 in the presence and absence of a potent CYP3A4 inhibitor.

5.1.3 Exploratory Objectives

Exploratory objectives of this trial include:

CCI

5.2 Endpoints

5.2.1 Primary Endpoint

The primary endpoint of the trial is the following PK parameters on Day 1 of Trial Period 1 and Day 4 of Trial Period 2:

- Maximum observed concentration (C_{max}).
- Area under the concentration-time curve from time 0 to infinity, calculated using the observed value of the last quantifiable concentration (AUC_{∞}).

5.2.2 Safety Endpoints

Safety endpoints include the following:

[figure not shown]
Safety and tolerability will be assessed through physical examinations, ECGs, vital signs, and laboratory assessments, and collection of spontaneous AEs.

5.2.3 Exploratory Endpoints

[figure not shown]
Exploratory endpoints will be assessed through the following parameters:

PK parameters:

CCI

CCI

Pharmacodynamic parameters:

CCI

6.0 TRIAL DESIGN AND DESCRIPTION

6.1 Trial Design

This is a phase 1, single-sequence, open-label, 2-period crossover trial in approximately 10 healthy male and female (non-childbearing potential) subjects. The trial is designed to investigate the effect of a potent CYP3A4 inhibitor (itraconazole) on the PK of TAK-954. TAK-954 0.2 mg will be administered as a single 60-minute IV infusion.

The trial will include a Screening Visit, Trial Period 1 (6 days), a washout (a minimum of 7 days between doses in Period 1 Day 1 and Period 2 Day 1), Trial Period 2 (9 days), and a Follow-up Visit. Blood samples for assessment of TAK-954 concentrations will be collected before each dose of TAK-954 and at intervals up to 120 hours after the last dose of trial drug in each trial period. Samples may be assayed for TAK-954 metabolites. TAK-954 and its metabolites will also be assayed in urine, data permitting and if deemed possible.

Whole blood samples for DNA PGx analysis and RNA isolation will be collected predose on Day 1 of Trial Period 1.

Safety will be assessed by monitoring for AEs, ECGs, vital signs, safety laboratory tests, and physical examinations throughout each dosing period.

CCI

After completion of the trial (or after subject withdrawal), all subjects will return for a Follow-up Visit, approximately 10 to 14 days after their last dose of trial drug.

6.2 Rationale for Trial Design, Dose, and Endpoints

6.2.1 Rationale of Trial Design and Dose

TAK-954 is a small molecule, 5-HT4 agonist. TAK-954 has been investigated in healthy subjects at single oral doses from 0.1 to 20 mg, multiple oral doses from 0.2 to 10 mg once daily (QD) for 10 days, and multiple IV doses from 0.1 to 0.5 mg QD for 5 days. A single IV dose of 0.5 mg TAK-954 has also been investigated in critically ill patients with enteral feeding intolerance and compared with metoclopramide. After multiple IV infusion dosing in healthy subjects (0.1 and 0.5 mg with a 1-hour infusion), TAK-954 concentrations declined in a biphasic manner, with mean $t_{1/2}$ values ranging from 18.0 to 18.9 hours on Day 5. TAK-954 steady state was achieved by Day 3 with minimal accumulation of TAK-954 after multiple IV dosing of 0.5 mg. The increase in exposure from the 0.1 mg to 0.5 mg IV dose was approximately dose proportional, and the mean amount of TAK-954 excreted unchanged in urine on Day 5 ranged from 27.7% to 31.6%. In subjects who were critically ill and received 0.5 mg by IV infusion, the PK exposure was slightly lower relative to that observed in healthy subjects.

Two active metabolites were identified nonclinically, but TAK-954 was not extensively metabolized to either of these metabolites after oral dosing (mean C_{max} and area under the concentration-time curve from time 0 to 48 hours metabolite to parent ratios ranged from 0.0008 to

0.004). Renal excretion of these metabolites was also low with concentrations in urine generally below the limit of detection. Evidence of GI prokinetic activity in healthy subjects (increased bowel movement frequency, looser stool consistency, and decreased time to first bowel movement) was observed at all dose levels after receiving single and multiple doses (oral and IV). In 7 subjects who were critically ill, scintigraphy data qualitatively suggest TAK-954 decreases gastric emptying time after a liquid meal.

After multiple oral doses in healthy subjects, TAK-954 was generally well tolerated at doses up to 5 mg QD for 10 days. There were no SAEs and the overall incidence of AEs reported for the TAK-954 dose groups was similar to that for the placebo group. All AEs were mild or moderate. The most commonly reported treatment-related AEs in TAK-954 subjects overall were headache and diarrhea. No dose-related trends were evident in the AE data across the 0.2, 1, or 5 mg dose groups, but 2 of 3 subjects receiving 10 mg were discontinued because of an AE (mild intermittent atrioventricular dissociation, which resolved without intervention). There were no safety signals in the clinical laboratory or respiratory rate data after multiple dose administration. Mean blood pressure (BP) and heart rate (HR) remained in the normal range for all groups throughout the trial. However, there was a trend toward lower BP and elevated HR in the standing position for TAK-954 subjects, but no dose response was apparent. In addition, there was one AE related to BP (orthostatic hypotension in a subject who received 5 mg TAK-954).

After IV doses in healthy subjects, TAK-954 was generally well tolerated at doses ranging from 0.1 to 0.5 mg QD for 5 consecutive days. No serious adverse events (SAEs) were reported. The most common AEs (ie, headache and postural dizziness) were not clinically significant and resolved spontaneously. Among the AEs reported, 3 subjects experienced modest and transient cardiovascular AEs upon standing after the first dose (ie, postural tachycardia and postural dizziness) that resolved spontaneously, and were not observed upon challenge. After single infusions of TAK-954 0.5 mg in subjects who were critically ill with enteral feeding intolerance, no subjects had an AE that led to trial discontinuation or interruption of treatment. Vital sign changes from Baseline noted during treatment were minimal and typical of critically ill subjects. No clinically relevant changes in ECGs in either treatment group were observed.

TAK-954 has been shown to undergo oxidative metabolism in vitro in human liver microsomes, though it was relatively stable when incubated with cryopreserved human hepatocytes ($t_{1/2} > 17$ hours).

The purpose of this trial is to investigate the effect of a potent CYP3A4 inhibitor on the PK of IV TAK-954 in healthy subjects. Itraconazole has been chosen as it is recommended by the FDA and EMA as a suitable potent CYP3A4 inhibitor for use in DDI studies. An IV dose of 0.2 mg TAK-954 has been selected as a dose that is predicted to be within the clinically relevant range, but is lower than the maximum multiple IV dose (0.5 mg) that has been investigated so far, to allow for any increases in exposure that may be observed with metabolic inhibition.

6.2.2 Rationale for Endpoints

6.2.2.1 PK

The primary endpoint for this trial consists of standard PK variables (C_{\max} and AUC_{∞}) to determine the effect of itraconazole on the PK of TAK-954 in healthy subjects.

6.2.2.2 Safety Endpoints

Key safety endpoints will be assessed through monitoring of AEs, vital signs, ECGs, clinical laboratory results, and physical examinations.

6.2.2.3 Exploratory Endpoints

CC1

6.2.3 Critical Procedures Based on Trial Objectives: Timing of Procedures

For this trial, the collections of the blood samples for TAK-954 (PK) are the critical procedures.

- At any postdose time point, the blood samples for TAK-954 (PK) needs to be collected as close to the exact nominal time point as possible.
- All other procedures should be completed as close as possible, either before or after the prescribed/scheduled time.
 - ECG and vital signs measurements should be performed before the nominal time of the TAK-954 (PK) if scheduled together.
- The order of priority can be changed during the trial with joint agreement of the investigator and the sponsor.
- Any nonscheduled procedures required for urgent evaluation of safety concerns take precedence over all routine scheduled procedures.

6.3 Trial Beginning and End/Completion

6.3.1 Definition of Beginning of the Trial

The overall trial begins when the first subject signs the trial informed consent form.

6.3.2 Definition of End of the Trial

The overall trial ends when the last subject completes the last planned or follow-up visit/interaction associated with a planned visit (this can be a phone contact), discontinues from the trial or is lost to follow-up (ie, the investigator is unable to contact the subject).

6.3.3 Definition of Trial Discontinuation

Trial discontinuation because of nonsafety reasons, such as:

- A finding (eg, PK, PD, efficacy, biologic targets) from another nonclinical or clinical trial using the trial treatment(s) results in the trial being stopped for a non–safety-related reason.
- Data from comparator(s), drug(s) of the same class, or methodology(ies) used in this trial become available and results in the trial being stopped for a non–safety-related reason.
- The trial is stopped because of nonscientific and nonsafety reasons, such as slow enrollment.

Trial discontinuation because of safety reasons:

- Early trial termination because of unanticipated concerns of safety to the trial subjects arising from clinical or preclinical trials with the trial treatment(s), comparator(s), drug(s) of the same class, or methodology(ies) used in this trial.

6.3.4 Criteria for Premature Termination or Suspension of the Trial

6.3.4.1 Criteria for Premature Termination or Suspension of Trial Sites

A trial site may be terminated prematurely or suspended if the site (including the investigator) is found in significant violation of GCP, protocol, or contractual agreement, is unable to ensure adequate performance of the trial, or as otherwise permitted by the contractual agreement.

6.3.4.2 Procedures for Premature Termination or Suspension of the Trial or the Participation of Trial Site(s)

In the event that the sponsor, an institutional review board (IRB), or regulatory authority elects to terminate or suspend the trial or the participation of an investigational site, a trial-specific procedure for early termination or suspension will be provided by the sponsor; the procedure will be followed by applicable investigational sites during the course of termination or trial suspension.

7.0 SELECTION AND DISCONTINUATION/WITHDRAWAL OF SUBJECTS

7.1 Inclusion Criteria

In order to be eligible for participation in this trial, the subject must:

1. Understand the trial procedures and agree to participate by providing written informed consent.
2. Be willing and able to comply with all trial procedures and restrictions.
3. Be a man or woman (with no child bearing potential) aged 18 to 55 years, inclusive, at the Screening Visit.
4. Have a BMI ≥ 18 and ≤ 30 kg/m² and a body weight >50 kg at the Screening Visit.
5. Be a nonsmoker who has not used tobacco- or nicotine-containing products (eg, nicotine patch) for at least 6 months before administration of the initial dose of trial drug/invasive procedure.
6. Be judged to be in good health by the investigator, based on clinical evaluations including laboratory safety tests, medical history, physical examination, 12-lead ECG, and vital sign measurements performed at the Screening Visit and before administration of the initial dose of trial drug.
7. Meet the following birth control requirements:
 - Is a male subject who is sterile or agrees to use an appropriate method of contraception, including a condom with or without spermicidal cream or jelly, from trial drug administration on the first day of the first dose until 5 half-lives plus 90 days after administration of the last dose of trial drug. No restrictions are required for a vasectomized male subject provided the subject is at least 1 year post–bilateral vasectomy procedure before trial drug administration on the first day of the first dose. A male subject whose vasectomy procedure was performed less than 1 year before trial drug administration on the first day of the first dose must follow the same restrictions as a nonvasectomized man. Appropriate documentation of surgical procedure should be provided.
 - Is a male subject who agrees to not donate sperm from trial drug administration on the first day of the first dose until 5 half-lives plus 90 days after administration of the last dose of trial drug.
 - Is a female subject with no childbearing potential, defined by at least 1 of the following criteria:
 - a) Postmenopausal (defined as 12 months of spontaneous amenorrhea in females aged >45 years, 6 months of spontaneous amenorrhea in females aged >45 years with serum FSH levels >40 mIU/mL). Appropriate documentation of FSH levels is required.
 - b) Surgically sterile by hysterectomy and/or bilateral oophorectomy with appropriate documentation of surgical procedure.

- c) Had a tubal ligation with appropriate documentation of surgical procedure.
- d) Has a congenital condition resulting in no uterus.

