3.0 SCHEDULE OF TRIAL PROCEDURES

Assessment	Screening	Trial Period 1 (a)						Trial Period 2							Follow-up/Early Termination		
		Day	-28 to -2	-1	1	2	3	4 to 6	-1	1	2 to 3	4	5	6	7	8	9
Administrative Procedures																	10-14 days after last dose of trial drug
Informed consent	X																
Inclusion/exclusion criteria	X	X															
Medical history/demographics	X																
Prior and concomitant medication review			-----Continuous review-----														
Clinic Procedures/Assessments																	
Full physical examination	X	X															X
Semirecumbent vital signs (heart rate [HR], systolic blood pressure [SBP] and diastolic blood pressure [DBP])	X		X(b)	X	X			X	X	X	X	X	X			X	X
Vital signs (respiratory rate, oral [at the floor of the mouth]/tympanic temperature) rate	X		X(b)					X									
Height	X																
Weight	X																
Body mass index (BMI)	X																
Standard 12-lead electrocardiogram (ECG)	X		X(b)		X		X				X				X		X
CCI																	
Adverse event (AE) monitoring			-----Continuous review-----														
Laboratory Procedures/Assessments																	
Serum chemistry	X	X			X		X							X			X
Hematology	X	X			X		X							X			X
Urinalysis	X	X			X		X						X			X	
Serum follicle-stimulating	X																

CONFIDENTIAL

Assessment	Screening	Trial Period 1 (a)						Trial Period 2						Follow-up/Early Termination		
		-28 to -2	-1	1	2	3	4 to 6	-1	1	2 to 3	4	5	6	7	8	9
Day	-28 to -2	-1	1	2	3	4 to 6	-1	1	2 to 3	4	5	6	7	8	9	10-14 days after last dose of trial drug
hormone (FSH)																
Urine drug screen	X	X					X									
Urine alcohol test/alcohol breath test (d)	X	X					X									
HIV test	X															
Hepatitis panel	X															
Pharmacokinetics (PK) Evaluations																
Plasma samples for TAK-954 (e)			X	X	X	X				X	X	X	X	X	X	
Urine sample for TAK-954 PK (f)			X	X	X					X	X	X				
Pharmacogenomic (PGx) Evaluations																
Blood sample for DNA PGx			X													
Blood sample for RNA PGx			X													
Drug Administration																
TAK-954 dosing			X								X					
Itraconazole dosing								X	X	X	X	X	X	X		
Other																
Confinement		X	X	X	X			X	X	X	X	X	X	X		
Meals		X	X	X	X			X	X	X	X	X	X	X		

(a) A minimum of 7 days between doses in Period 1 Day 1 and Period 2 Day 1.

(b) Assessments at predose (within 30 minutes), 1, 2, 4, 8, and 12 hours postdose (relative to TAK-954 start of infusion).

(c) CCI

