7.2 Exclusion Criteria

The subject must be excluded from participating in the trial if the subject:

- 1. Has a history of clinically significant endocrine, gastrointestinal (including motility disorder and intestinal obstruction), cardiovascular, hematological, hepatic, immunological, renal, respiratory, genitourinary, or major neurological (including stroke and chronic seizures) abnormalities or diseases.
- 2. Has participated in another investigational trial within 4 weeks before the pretrial (Screening) visit. The 4-week window will be derived from the date of the last trial procedure and/or AE related to the trial procedure in the previous trial to the pretrial/Screening Visit of the current trial.
- 3. Is an employee or immediate family member (eg, spouse, parent, child, sibling) of the sponsor.
- 4. Has a history of cancer (malignancy).
- 5. Has a history of significant multiple and/or severe allergies (eg, food, drug, latex allergy) or has had an anaphylactic reaction or significant intolerance to prescription or nonprescription drugs or food.
- 6. Has a positive alcohol or drug screen.
- 7. Is a lactating/nursing woman.
- 8. Had major surgery, donated or lost 1 unit of blood (approximately 500 mL) within 8 weeks of the first dose of trial drug.
- 9. Has a known hypersensitivity to any component of the formulation of TAK-954 or related compounds, or to itraconazole (see Product Insert).
- 10. Is unable to refrain from or anticipates the use of any medication, including prescription and nonprescription drugs or herbal remedies, beginning approximately 7 days before administration of the initial dose of trial drug, throughout the trial (including washout intervals between trial periods), until the Follow-up Visit. There may be certain medications that are permitted, see Section [7.3](#).
- 11. Has a history of alcohol consumption exceeding 2 standard drinks per day on average (1 glass is approximately equivalent to: beer [354 mL/12 ounces], wine [118 mL/4 ounces], or distilled spirits [29.5 mL/1 ounce] per day).
- 12. Consumes excessive amounts, defined as greater than 6 servings (1 serving is approximately equivalent to 120 mg of caffeine) of coffee, tea, cola, energy drinks, or other caffeinated beverages per day.
- 13. Has a substance abuse disorder.

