9.2.1.2 Screening

Serum

Serum evaluations will include the following tests:

HIV test	FSH (females only)
	Hepatitis panel, including HBsAg and anti-HCV

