Appendix D Pregnancy and Contraception **Contraception and Pregnancy Avoidance Procedure**

Female Subjects and Their Male Partners

Female subjects of childbearing potential are excluded from this trial; there are no requirements for contraception or pregnancy avoidance.

Male Subjects and Their Female Partners

From signing of informed consent, throughout the duration of the trial, and for 5 half-lives PLUS 90 days after the last dose of trial drug, nonsterilized** male subjects who are sexually active with a female partner of childbearing potential must use barrier contraception (eg, condom with or without spermicidal cream or jelly). In addition, they must be advised not to donate sperm during this period. Women of childbearing potential who are partners of male subjects are also advised to use additional contraception as shown in the list containing highly effective/effective contraception below.

** Sterilized males should be at least 1 year post-bilateral vasectomy and have confirmed that they have obtained documentation of the absence of sperm in the ejaculate or have had bilateral orchidectomy.

1. Highly effective methods of contraception are defined as “those, alone or in combination, that result in a low failure rate (ie, less than 1% failure rate per year when used consistently and correctly). In this trial, where medications and devices containing hormones are included, females of childbearing potential who are partners of male subjects are advised to use additional contraception chosen from the list below:
 - Nonhormonal methods:
 - Intrauterine device.
 - Bilateral tubal occlusion.
 - Hormonal methods:
 - Combined (estrogen and progestogen) hormonal contraception associated with inhibition of ovulation initiated at least 3 months before the first dose of trial drug.
 - Oral.
 - Intravaginal (eg, ring).
 - Transdermal.
 - Progestogen-only hormonal contraception associated with inhibition of ovulation initiated at least 3 months before the first dose of trial drug.
 - Oral.
 - Injectable.

➤ Implantable.

2. Since genotoxicity/teratogenicity/embryotoxicity is unlikely to be caused by the investigational drug, additional effective methods of contraception (there may be a higher than 1% failure rate) that may be chosen by the female partner of a male subject are:
 - Double-barrier method (contraceptive sponge, diaphragm or cervical cap with spermicidal jellies or creams).

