8.0 REFERENCES

Appendix A Schedule of Study Procedures

Assessment	Screening	Trial Period 1 (a)						Trial Period 2							Follow-up/Early Termination		
		Day	-28 to -2	-1	1	2	3	4 to 6	-1	1	2 to 3	4	5	6	7	8	9
Administrative Procedures																	10-14 days after last dose of trial drug
Informed consent	X																
Inclusion/exclusion criteria	X		X														
Medical history/demographics	X																
Prior and concomitant medication review																	
Clinic Procedures/Assessments																	
Full physical examination	X	X															X
Semirecumbent vital signs (heart rate [HR], systolic blood pressure [SBP] and diastolic blood pressure [DBP])	X		X(b)	X	X			X	X	X	X(b)	X	X			X	X
Vital signs (respiratory rate, oral [at the floor of the mouth]/tympanic temperature) rate	X		X(b)					X									
Height	X																
Weight	X																
Body mass index (BMI)	X																
Standard 12-lead electrocardiogram (ECG)	X		X(b)		X			X			X(b)					X	X
Bowel movement assessment (c)			X	X	X			X	X	X							
Adverse event (AE) monitoring																	
Laboratory Procedures/Assessments																	
Serum chemistry	X	X			X		X							X			X
Hematology	X	X			X		X							X			X
Urinalysis	X	X			X		X							X			X
Serum follicle-stimulating	X																

CONFIDENTIAL

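### Women admitted on documented tubal ligation alone have no required pregnancy test, in the visible text, before 10 trial doses; a β-hCG assay on chemistry serum would close this small safety gap (minor)

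*Protocol*

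**What the plan says.** **Eligibility.** Section 7.1, item 7, accepts a woman who meets any one of four criteria. Criterion (c) is "Had a tubal ligation with appropriate documentation of surgical procedure". The others are menopause, hysterectomy and/or bilateral oophorectomy, and congenital absence of the uterus.

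**Exclusion and withdrawal.** Section 7.2, item 7, reads "Is a lactating/nursing woman" and does not mention pregnancy. Section 7.5 has no criterion that names pregnancy.

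**Tests.** Section 9.2.1 lists chemistry, hematology, urinalysis, drug screen, alcohol screen, HIV, hepatitis and, for women only, FSH. There is no pregnancy test. Protocol Section 3.0 and SAP Appendix A have no row for one, and SAP Section 7.11.2 lists none.

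**Appendix D.** For female subjects, "there are no requirements for contraception or pregnancy avoidance". For female partners of childbearing potential, it lists "Bilateral tubal occlusion" among highly effective methods, defined as those "that result in a low failure rate (ie, less than 1% failure rate per year when used consistently and correctly".

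**Exposure.** The Trial Summary gives two TAK-954 doses and eight itraconazole doses. Section 4.3 expects no clinical benefit for participants.

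**The concern.** Criteria (b) and (d) describe anatomy or surgery that leaves no uterus or no ovaries. Tubal ligation leaves both, and Appendix D itself treats tubal occlusion as contraception with a residual failure rate. FSH, the only test specific to women, supports criterion (a) and says nothing about (c).

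The evidence asked of the two sexes also differs. A vasectomized man is exempt from contraception only from one year after the procedure, and Appendix D also asks for documented absence of sperm. A 7(c) woman needs only her surgical record, subject to the general bar on major surgery within 8 weeks of first dose.

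At stake is an unrecognised early pregnancy exposed to as many as 10 doses in a trial with no expected benefit to the participant. This is a safety point only. It does not touch Cmax, AUC∞ or the sample size.

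**Working it through.** **1. Dose count.** TAK-954: Period 1 Day 1 and Period 2 Day 4 = 2. Itraconazole: daily on Period 2 Days 1 to 8 = 8. Total 10, matching the Trial Summary.

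**2. Does a redaction hide a test?** One row of the protocol schedule is blacked out. In SAP Appendix A the row in the same position is legible and is the bowel movement assessment. The redaction therefore does not account for the missing test.

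**3. Is serum already drawn at the right visits?** In the protocol schedule, the chemistry marks read in order as Screening, Period 1 Day -1, Period 1 Day 3 and Period 2 Day -1, followed by later marks. The fourth mark shares a column with the Period 2 drug screen, one column before the first itraconazole dose. This relies on the extracted table.

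**4. Order of magnitude.** The documents give no ligation failure rate. The only usable figure is the Appendix D class ceiling of 1% per year, spread evenly over time (an assumption):

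risk per woman ≤ 0.01 × days / 365

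The calendar uses the minimum 7-day washout and sets Screening on Day -28 as d0. Then Period 1 Day -1 = d27, Period 1 Day 1 = d28, Period 2 Day -1 = d34, Period 2 Day 1 = d35, and the last itraconazole dose = d42. Adding 10 to 14 days of follow-up gives 52 to 56 days, within the stated 7 to 8 weeks (49 to 56 days).

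| Window to last dose | Days | Ceiling per woman |
|---|---|---|
| Screening on Day -2 (d26), minimum washout | 42 − 26 = 16 | 0.04% |
| Shortest stated evaluation less longest follow-up | 49 − 14 = 35 | 0.10% |
| Screening on Day -28, minimum washout | 42 | 0.12% |
| Longest stated evaluation less shortest follow-up | 56 − 10 = 46 | 0.13% |
| Pregnancy unrecognised for 56 days before first dose (assumption) | 56 + 14 = 70 | 0.19% |

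The number of 7(c) women is not given. Taking 0 to 10 of the 10 planned subjects and the 42-day window, the chance of at least one pregnancy is at most 0% to 1 − (1 − 0.00115)^10 = 1.1%. The upper end, with every subject a 7(c) woman, is an extreme.

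**5. What testing could catch.** On the 42-day calendar the last test falls on d34, so conceptions in the final 42 − 34 = 8 days (19%) are out of reach. If hCG becomes detectable 0 to 14 days after conception (assumption), conceptions in 34 down to 20 of the 42 days (81% to 48%) could be caught. The Period 2 test precedes 9 of the 10 doses.

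**The case against.** The strongest reply is that this is a stated and self-consistent choice. The protocol defines documented ligation as absence of childbearing potential, excludes women of childbearing potential, and so asks nothing more of female subjects. The Appendix D listing is written for partners, who are neither screened nor asked for surgical records. That stands as far as it goes: a reader might infer that the protocol contradicts itself, but the two passages serve different purposes. What remains is that the same kind of procedure carries an acknowledged failure rate in one place and is accepted without a test in the other.

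Other stronger readings also go too far:

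- *A planned test was dropped.* β-hCG is defined in both abbreviation lists and used nowhere in the visible text. So are MTD and EFI, which points to template carry-over.
- *Pregnant women may enrol.* A known pregnancy would already conflict with inclusion 3, and inclusion 6 requires a judgement of good health. Neither requires a test, however.
- *The drugs endanger a fetus.* Appendix D calls embryotoxicity unlikely for the investigational drug. The visible text does not address itraconazole in this respect, and its insert was not supplied.
- *A pregnancy found later has no consequence.* Section 7.5, item 3, allows withdrawal when a subject is found not to have met entry criteria and continuing poses unacceptable risk. This partly covers the case.

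Finally, the text following the supplied part of Appendix D was not available and may contain pregnancy provisions. The conclusion is confined to the visible text.

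**Conclusion.** A minor point, best described as a cheap safety improvement. Within the visible text, a woman can enter on documented ligation alone and receive all 10 doses without a required pregnancy test.

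The actual risk cannot be computed, because the documents give neither a ligation failure rate nor the number of 7(c) women. The class ceiling supports only a statement of scale: at most the order of 0.1% per such woman. The decimals in the table show how the window matters and should not be read as estimates for this trial. The case for acting rests on the low cost of the test and the absence of expected benefit to participants, not on a demonstrated hazard.

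**What to change.** - Add serum β-hCG for women admitted under 7(c), including replacements, to Section 9.2.1, Protocol Section 3.0 and SAP Appendix A, at Screening, Period 1 Day -1 and Period 2 Day -1.
- Require a negative result before dosing in each period.
- Reword exclusion 7 as *Is a pregnant or lactating/nursing woman*. This gives a positive result a defined consequence, but detects no one without the test.
- Optionally name a positive test in Section 7.5. The eligibility row has no mark in Period 2, but item 3 of that section already goes part of the way.

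**Cost.** Amendment wording and up to three assays per 7(c) woman, on serum already drawn, with no new visit. Dosing falls between 0600 and 0900, so each Day -1 result must be back by the next morning. If separate tubes were needed (assumed 2 to 5 mL each), total blood would rise from about 300 mL to 300 + 3×2 = 306 mL or 300 + 3×5 = 315 mL, under the 500 mL limit in Section 4.3. Conceptions after, or just before, Period 2 Day -1 would still be missed. Eligibility changes only for a pregnant woman.
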